#### **4.5. Analysis of Substudy Endpoint(s)**

*Substudy Aim 1: Examine the test-retest reliability of at-home instrumented physical performance tests*

Test retest reliability of sensor metrics derived during the two sets of at-home physical performance tests (7-meter gait task, 5 times sit to stand tasks) will be assessed using ICC and correlation analyses. Pearson's product-moment correlations or Spearman's rank order correlations will be used depending on their normality. These analyses will be conducted on all sensor metrics derived from the 3-sensor IMU system and GaitPy and Sit2StandPy applied to the lumbar sensor (Tables 3. and 4.).

*Substudy Aim 2: Examine agreement between wearable sensor data collected during in-lab and at-home instrumented physical performance tests*

We will assess agreement between wearable sensor metrics collected in-lab and those collected at-home during the same physical performance tests (7-meter gait, 5 times sit to stand) from the 3-sensor IMU system and the lumbar sensor separately. Agreement will be assessed using ICC analyses as well as Bland–Altman plots and 95% limits of agreement between at-home and in-clinic sensor metrics for both systems (using metrics listed in Tables 3. and 4.).

As stated in the protocol, these analyses will be performed on a subset of participants (n=12). Once 12 participants have had the opportunity to complete the study, an interim analysis may be conducted (while continuing to enroll) to determine if additional participants are required to address the aims of this substudy.

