6. STUDY INTERVENTION AND ASSESSMENTS

6a. MAIN STUDY

Recruitment and screening:

Participants will be recruited through multiple channels (flyers, newspaper advertisements, clinical data warehouse, etc.) including via social media using Trialfacts. Screening will occur via a 4-step process. Step 1 will be online pre-

screening using Trialfacts screening webpage. Those eligible will then undergo telephone pre-screening as step 2. Step 3 would be obtaining confirmation of knee OA diagnosis from the participant's physician along with clearance to participate in an exercise program. Step 4 will be an in-lab visit (part of baseline visit) to confirm BMI eligibility. If in-lab screening visit is not possible due to COVID-19, BMI eligibility will be determined from the physician diagnosis letter that includes a most recent height and weight.

COVID-19 Screening: Prior to all in-lab and in-clinic visits, participants will be screened for potential exposure to COVID-19 using BU mandated protocols. Participants will be called prior to their visit to determine if they have any COVID-19 related symptoms, if they have been in close contact with a known or suspected COVID-19 positive case, request they take their temperature prior to their appointment, and inform participants to call the lab/clinic if they develop any COVID related symptoms prior to their visit. In addition, participants will undergo symptom and temperature screen in person when they arrive for lab/clinic visits. Participants will be required to wear a face mask during the entire visit and perform hand hygiene before entering the lab. This screening will remain in place until Boston University guidelines recommend discontinuation of its use.

Informed consent: Most participant consents will be completed in-person during the baseline in-lab visit. For participants in the substudy randomized to completing the baseline at-home visit prior to the baseline in-lab visit (n=6-10), the informed consent will be obtained during an additional in-lab visit specifically for BMI screening, obtaining consent and providing tablet computer and sensors. If the in-lab visit is not possible due to COVID-19 related restrictions, the informed consent will be obtained remotely via REDCap and video call.

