2. Examine agreement between wearable sensor data collected during in-lab and at-home physical performance tests

Participants will be wearing a 3-sensor inertial system in addition to the lumbar sensor.

Recruitment and screening: Participants from the parent study who are able to attend a baseline visit in-lab will be asked to participate in the substudy, for up to a total sample size of 20.

Substudy sample size: The size of the substudy was based on data collected from a group of healthy adults (n=32, [65-85] years old). Test-retest reliability of gait metrics between two lab visits derived from lumbar sensor data using the GaitPy algorithm (Czech et al., 2019) and calculated using the intraclass correlation coefficient (ICC) was 0.85 [0.71 0.92] for gait speed. To be able to replicate these substantial ICC values between two at-home assessments, we estimate that we need at least 11 participants (based on ICC H_0 of 0.42 computed by generating a null distribution based on 10,000 permutations of the gait speed across subjects between visit 1 and visit 2 and taking the 99th percentile of this distribution as ICC H_0 ; an ICC of 0.85, and using a one-tailed test with alpha=0.05 and power=0.8; Computed using R package ICC.Sample.Size; Zou, 2012).

Considering 10% attrition, we estimate that 12 participants are required for this substudy.

We will undertake interim analysis after 12 participants have completed the substudy (while continuing to enroll) to determine if additional participants are required to address the aims of this substudy.

Assessments: Participants will be asked to participate in 2 assessments of which 1 will be in-lab and 1 will be at-home. The order of these assessments will be randomized and occur within 2-weeks of each other.

At-home Visit

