7. ANALYSIS PLAN

7.1. Analysis of Primary Aim and Endpoints

Details of the analysis of this study will be documented in the Statistical Analysis Plan (SAP). The analyses described in the approved SAP will be followed if different from what is described in this protocol.

Primary Aim: Measure the effect of PT on functional performance using digital measures from wearable sensors.

The following analyses will be performed to address this primary aim.

A. Validate wearable sensor-based metrics of functional biomechanical tests in people with knee OA against optical motion capture

Data from the lumbar sensor and optical motion capture during gait and sit-to-stand tasks during in-lab visits will be used for this analysis. Wearable sensor metrics will be compared against gold standard metrics from the optical motion capture system using intra-class correlation coefficient (ICC) and its 95% lower and upper confidence limits. The ICC reflects both the degree of correlation and agreement between the measurements. We will interpret agreement between measurements according to the following benchmarks: $ICC \leq 0.4$ indicates 'poor', 0.4 to 0.59 'moderate', 0.6 to 0.74 'good', and 0.75 to 1 'excellent' reliability (Cicchetti et al., 1994). In addition, we will also compute the mean, variance and percentage error between the standard and the digital measurements. Bland–Altman plots and 95% limits of agreement (average difference ± 1.96 standard deviation of the difference) will also be computed.

B. Compare wearable sensor-based metrics of physical performance in people with knee OA with standardized physical performance outcomes.

Wearable sensors with excellent reliability from analysis A will be examined. Sensor-based metrics from lumbar sensor during physical performance tests in-lab will be correlated with standardized physical performance outcomes using Pearson's product-moment correlations or Spearman's rank order correlations depending on their normality.

C. Assess the effects of exercise-based PT on outcomes from wearable sensors during in-lab physical performance tests

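### The home-versus-lab agreement analysis makes no use of the randomised visit order and gives no confidence intervals for its limits of agreement (minor)

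*SAP*

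**What the plan says.** Protocol section 6a (Substudy, Assessments) has each participant tested once in the lab and once at home: "The order of these assessments will be randomized and occur within 2-weeks of each other". At the home visit all tests are done, the sensors come off for 15 minutes, and everything is then repeated, so there are two home sets and one lab set.

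The informed-consent paragraph of protocol section 6a expects a home-first group: "For participants in the substudy randomized to completing the baseline at-home visit prior to the baseline in-lab visit (n=6-10"). The compensation table (protocol section 10) estimates 5-10 consent visits for that group and 11-20 substudy home visits. No allocation ratio or blocking is given.

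For the analysis, SAP 4.5 states: "We will assess agreement between wearable sensor metrics collected in-lab and those collected at-home during the same physical performance tests". Like protocol 7.4, it names the ICC, Bland-Altman plots and 95% limits of agreement, with no order, period or sequence term. It does not say which home set enters the comparison, and it plans no confidence intervals for the limits. SAP 4.5 puts the number analysed at 12, with a possible interim look to decide on more; the protocol allows up to 20.

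The substudy sections do not define the limits. The only definition in either document belongs to primary analysis A, the comparison with motion capture (protocol 7.1 A; SAP 4.2 A): "95% limits of agreement (average difference ± 1.96 standard deviation of the difference").

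**The concern.** The design collects the information needed to separate location from session order, and the analysis does not use it. A second-session effect, such as practice or familiarity with the devices, enters the home-minus-lab difference with a positive sign when home comes second and a negative sign when it comes first. Pooling the two groups turns a systematic effect into apparent random disagreement. Home testing could then look less interchangeable with lab testing than it is. If the groups come out unequal, part of the effect also moves into the mean difference.

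The second matter is how the limits are stated. With about 12 people the SD is poorly estimated, and limits given without intervals look firmer than they are.

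**Working it through.** **The plan's own figure.** The substudy size rests on a test-retest ICC test, which is Aim 1, with two repeats: a null "based on ICC H_0 of 0.42 computed by generating a null distribution based on 10,000 permutations" against "an ICC of 0.85, and using a one-tailed test with alpha=0.05 and power=0.8". The formula is n = 1 + 2k(z_α + z_β)² / [(k-1)(ln C)²], where C = (1 + kθ0)/(1 + kθ1), θ = ICC/(1 - ICC) and k = 2.

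- θ0 = 0.42/0.58 = 0.724 and θ1 = 0.85/0.15 = 5.667
- C = 2.448/12.333 = 0.1985, so ln C = -1.617
- n = 1 + 4 × (1.645 + 0.842)²/1.617² = 10.46, which rounds up to the stated 11

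The figure reproduces. It says nothing about the precision of the Aim 2 limits, for which no calculation is given.

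**Model for order.** Let d = home minus lab, δ the location difference, σ the SD of d within an order group, and π the second-session effect in units of σ. Set σ = 1. Then d has mean δ + π if home is second and δ - π if home is first. The documents give no π; 0.25, 0.5 and 1.0 are assumptions.

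**Mean difference.** Bias = π × (n_home-second - n_home-first)/n.

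- 6:6 gives 0 for any π
- 7:5 gives π × 2/12 = π/6
- 8:4 gives π × 4/12 = π/3, or 0.17 SD when π = 0.5

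The range 6-10 is half of 12-20, so roughly 1:1 is intended. If that meant simple randomisation of 12, an 8:4 or more unequal split (either way) would have probability 0.39.

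**SD and ICC under balanced order.** Pooled SD = √(1 + π²). For the ICC, take the plan's 0.85 as the true value purely for illustration. With total variance 1, the between-person mean square is 2 × 0.85 + 0.15 = 1.85, the error mean square is 0.15(1 + π²), and the ICC is their difference over their sum.

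| π (assumed) | SD multiplier | Error mean square | ICC |
|---|---|---|---|
| 0 | 1.00 | 0.150 | 0.85 |
| 0.25 | 1.03 | 0.159 | 0.84 |
| 0.5 | 1.12 | 0.188 | 0.82 |
| 1.0 | 1.41 | 0.300 | 0.72 |

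**Limits, no period effect.** For normal differences, the expected share of new differences inside mean ± 1.96 SD is P(|t with n-1 df| < 1.96/√(1 + 1/n)). The half-width of the 95% CI for each limit is t(0.975, n-1) × √(1/n + 1.96²/(2(n-1))).

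| n | Expected coverage | CI half-width per limit |
|---|---|---|
| 12 | 91.4% | 2.201 × √(0.0833 + 0.1746) = 1.12 SD |
| 20 | 92.9% | 0.81 SD |

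With an order term the residual df is n-2. The t-based multiplier at n=12 is then t(0.975, 10) × √(1 + 1/12) = 2.228 × 1.041 = 2.32. The ratio to 1.96 is 1.18, so the limits are about 18% wider for the same SD.

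**Both together.** Simulated coverage of the pure location difference by ±1.96 SD limits, with order ignored, at n=12 split 6:6:

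| π (assumed) | Coverage |
|---|---|
| 0 | 91.3% |
| 0.25 | 92.2% |
| 0.5 | 94.4% |
| 1.0 | 98.4% |

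**The case against.** Randomising order is the standard protection against a period effect. A reader might infer that location is confounded with period here; the documents do not support that. The planned home-first numbers imply about 1:1, and at 6:6 the mean difference has no bias whatever the period effect. Pairing 6 home-first with a total of 20 would show a larger bias, but it joins the low end of one range to the high end of another. This part of the objection stands.

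A reader might also infer that the limits must under-cover. They need not: ignoring order widens them and 1.96 narrows them, as the last table shows. The two cancel only for one particular period effect, which is unknown, so this is no reason to leave both alone.

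Nor does SAP 4.5 itself state 1.96; carrying it over from analysis A is a reasonable inference. Mean ± 1.96 SD is the conventional definition and estimates the population limits. Coverage of a new difference is a different target, so conventional limits with confidence intervals are an acceptable answer.

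A large period effect may be unlikely. Protocol 2.3 describes practice trials before data collection, and staff guide the home tests by live video. Against that, home-first participants reach the lab having completed two full home sets. Finally, Aim 2 is estimation with no acceptance threshold, and enrolment can continue to 20. These points limit the consequence but do not explain leaving a randomised factor out of the analysis.

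**Conclusion.** The point holds as a minor one. Order is randomised and unused. The cost of that is a wider SD of the differences (3% to 41% over the assumed 0.25 to 1.0 SD), a lower ICC, and bias in the mean difference only if the split is unequal (one sixth of the effect at 7:5, one third at 8:4). If ±1.96 SD is carried over and there is no period effect, expected coverage is 91.4% at n=12 and 92.9% at n=20. The lack of confidence intervals matters more, since each limit is uncertain by about ±1.1 SD at n=12.

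This rests on normally distributed differences, on period-effect sizes that are assumptions, and on a second-session effect of equal size in both orders. If the effect differs by order, an order term cannot separate that difference from location. The SAP's silence on which home set is used is a related gap: using the second set, or an average, could mix repetition within the home visit with location even at 6:6.

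**What to change.** In SAP 4.5, Substudy Aim 2:

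1. Regress the paired home-minus-lab difference on order, coded +1 and -1 so that the intercept is the location difference. Fixed location and period effects with a random participant effect are equivalent. Report the order-adjusted mean difference and ICC.
2. Base the limits on the residual SD of the paired differences, with n-2 df. If the mixed model is used, multiply its residual SD by √2, because that SD refers to single measurements; without this the limits would be about 29% too narrow (1 - 1/√2).
3. State the multiplier, either 1.96 or t-based (about 2.32 at n=12), and give 95% CIs for both limits.
4. Compare the first at-home set with the lab set, so that repetition within the home visit is not mixed with location.
5. State the allocation ratio and any blocking.

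The cost is SAP wording, one degree of freedom, and limits up to about 18% wider at n=12 if the t multiplier is chosen. No new data are needed.

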*denotes that these tasks will be performed while wearing lumbar sensors, wrist sensors, and 8-sensors IMU system												
** denotes that these tasks will be performed while wearing lumbar sensors, wrist sensors, 8-sensors IMU system, optical motion capture markers, and EMG sensors												
§denotes that these tests will be administered at-home while wearing lumbar sensor, wrist sensor, and 3-sensor IMU system, only if in-lab visits are not possible												
#denotes that balance component of this test will not be performed if administered at-home												
ET = early termination visit												

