The wrist sensor will be worn on the non-dominant wrist until the end of the study at week 18. The lumbar sensor will be used for a week-long period and subsequently removed by the participants at home and mailed back to the site.

This visit will include physical performance tests (6-minute walk test, stair climbing test, 7-meter gait test, modified short-performance physical battery, and a 15 second step-up test). All of these tests will be done with the lumbar sensor, 8-sensor inertial system, and wrist sensor worn by the participant. In case this visit is done at-home, 6-minute walk test, stair climbing test, and balance and gait portion of modified short-performance physical battery will not be done. For the at-home visit, the tablet computer, a 3-sensor inertial system (both feet and trunk), lumbar sensor, and wrist sensor will be mailed to the participants ahead of time with detailed written and video instructions. Participants then will be instructed via live video calls on how to set-up and use these devices and also collect data for the baseline visit. An initial phone call may be used to help participants become familiar with Zoom.

Pain in the index knee will be assessed on a numeric rating scale (ranging from 0=No pain at all, to 10=Worst imaginable pain) at the start and end of the session. In addition, multiple patient-reported outcomes will be collected (see Table earlier).

Participants will undergo 3-D optical motion capture assessment during walking at self-selected pace, walking at fast pace, , getting up from a chair, and standing balance. The participants will be instrumented with lumbar sensor, 8-sensor inertial system, wrist sensor, optical motion capture sensors, and surface electromyography sensors. These tests will not be performed in at-home visit.

Participants will undergo assessment of strength in the quadriceps and hamstring muscles. These tests will not be performed in at-home visit.

Participants will also undergo Quantitative Sensory Testing (including an assessment of Exercise-Induced Hypoalgesia) for pain phenotyping. These tests will not be performed in a at-home visit.

This visit is expected to last approximately 4 hours 30 minutes if performed in-lab. This visit is expected to last approximately 1 hr 30 minutes if performed at-home.

Visit #2 (Week 6)

Participants will complete questionnaires (see table above) and undergo multiple assessments of function in the lab.

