Participants will be provided hardware including 3-sensor inertial system and lumbar sensor with detailed written and video instructions. Participants will also be provided with cones connected with a string that is 7-meters long for the gait test, a chair for the sit-to-stand tests, and a step-up box for the step-up tests. A tele-research visit will be scheduled during which the researchers will guide the participants through application of all sensors and the tests. Physical performance tests will include 7-meter gait test, 5 times sit to stand test (collected as part of the modified short-performance physical battery), and 15 second step-up test. All of these tests will be done with the lumbar sensor, 3-sensor inertial system, and wrist sensor worn by the participant. After the tests are complete the participants will be asked to remove all sensors and wait for 15-minutes during which time they may be asked to complete questionnaires described elsewhere. After 15-minutes, the participants will re-place all of the sensors and repeat all the activities. At the end of the tele-research visit, participants will be guided into removing the sensors and mail it back to the research team. The lumbar sensor may be kept on depending on whether the participants have already completed the in-person visit or not.

In-lab visit:

This is the same as the baseline visit in the parent study.

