Peak sagittal trunk angle (deg)
Peak medial quadriceps-medial hamstrings co-contraction
Peak knee adduction moment (%BodyWeight x Height)
Peak knee flexion moment (%BodyWeight x Height)
Peak knee flexion (deg)
Balance Measures
Center of pressure displacement in A-P direction (mm)
Center of pressure displacement in M-L direction (mm)
Mean center of pressure velocity (mm/s)

Strength Assessment

Participants' strength will be evaluated with an isokinetic dynamometer through tasks of knee flexion and extension on the side of the index joint. Tests include maximal isometric extension torque (x3), maximal isometric flexion torque (x3), isokinetic flexion-extension at 60 deg/s (x2), and isokinetic flexion-extension at 120 deg/s (x2). Additionally, isometric plantarflexion trials (x2) will be recorded for the purpose of EMG normalization.

Device to be used: Biodex System 3

Raw Data obtained:

- Torque
- Angular position
- Angular velocity

Derived measures:

- Isometric testing
 - Peak extensor torque (Nm/kg)
 - Peak flexor torque (Nm/kg)
- Isokinetic testing
 - Peak extensor torque at 60 deg/s (Nm/kg)
 - Peak flexor torque at 60 deg/s (Nm/kg)
 - Peak extensor torque at 120 deg/s (Nm/kg)
 - Peak flexor torque at 120 deg/s (Nm/kg)

In-lab Functional Assessments (only wrist and lumbar sensors will be worn during these tests):

- *Stair climbing test (SCT)*
 - Ascending and descending a flight of stairs (x2)
 - Will only be assessed during in-lab visits

- **6-minute walk test (6MWT)**
 - Distance covered in 6 minutes
 - Will only be assessed during in-lab visits
- **15-second step-up test:**
 - Number of step-ups in 15-second (4in step)
 - Will be assessed during both in-lab and at-home visits
- **7-meter gait test**
 - Get up from a chair, walk 7 meters, turn around, return to starting position, sit down
 - Will be assessed during both in-lab and at-home visits
- **Short Physical Performance Battery (SPPB).** SPPB includes the following tests
 - Balance tests (all performed with eyes open and under close supervision of a study staff member)
 - Side-by-side stand – standing with feet side-by-side for 10 seconds
 - Semi-tandem stand – standing with side of the heel of 1 foot touching the big toe of the other foot for 10 seconds
 - Tandem stand – standing with the heel of one foot in front of and touching the toes of the other foot for 10 seconds
 - Will only be assessed during in-lab visits
 - Gait speed test (x2)
 - walking over a 4-meter walkway

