### 3.4. Substudy Endpoints

*Substudy Aim 1: Examine the test-retest reliability of at-home instrumented physical performance tests*

*Substudy Aim 2: Examine agreement between wearable sensor data collected during in-lab and at-home instrumented physical performance tests*

**Table 3. Gait measures obtained from GaitPy algorithm applied on the lumbar sensor and from 3-sensor IMU System during the 7-meter walk tasks performed at home and in-lab**

	GaitPy applied on Lumbar Sensor 	3-sensor IMU system 
a.	Cadence (steps/min)	Cadence (steps/min)
b.	Step length symmetry	
c.	Gait speed (m/s)	Gait speed (m/s)
d.	Stride duration (s)	Gait cycle duration (s)
e.	Stride duration asymmetry (s)	
f.	Step duration (s)	Step duration (s)
g.	Step duration asymmetry (s)	
h.	Initial double support time (s)	
i.	Terminal double support time (s)	Terminal double support (% gait cycle, s)
j.	Total double support time (s)	Double support (% gait cycle, s)
k.	Single limb support time (s)	
l.	Stance time (s)	Stance phase (% gait cycle, s)
m.	Swing time (s)	Swing (% gait cycle, s)
n.	Step length (m)	
o.		Foot clearance (m)
p.		Lateral step variability
q.		Foot strike angle (deg)

r.		Toe off angle (deg)
s.		Toe out angle (deg)
t.		Turning angle (deg)
u.		Turning duration (s)
v.		Turning velocity (deg/s)

**Table 4. Sit-to-stand measures derived from Sit2StandPy algorithm applied on the lumbar sensor and from the 3-sensor IMU system during the 5 times sit-to-stand tasks performed at home**

	Sit2StandPy applied on Lumbar Sensor	3-sensor IMU system^16
a.	Number of sit-to-stands	
b.	Sit-to-stand duration (s)	Sit-to-stand duration (s)
c.	Maximum acceleration (m/s  )	
d.	Minimum acceleration (m/s  )	
e.	SPARC: SPectral ARC length	
f.		Stand-to-sit duration (s)

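### Substudy Aim 2: the documents conflict on which inertial system supplies the in-lab 3-sensor metrics, and the two-visit window is not closed by the start of PT

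*SAP*

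**What the plan says.** SAP 4.5 plans ICCs, Bland-Altman plots and limits of agreement between in-lab and at-home metrics for the 7-meter gait and 5 times sit-to-stand tests, "from the 3-sensor IMU system and the lumbar sensor separately". The SAP Table 3 title agrees, listing gait metrics from the "3-sensor IMU System during the 7-meter walk tasks performed at home and in-lab". The Table 4 title covers only metrics "from the 3-sensor IMU system during the 5 times sit-to-stand tasks performed at home", although SAP 4.5 uses that table for the in-lab versus at-home comparison too.

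The protocol gives several accounts of what is worn in-lab:

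- The substudy part of section 6a says of the in-lab visit: "This is the same as the baseline visit in the parent study". Visit #1 in the main-study part says: "All of these tests will be done with the lumbar sensor, 8-sensor inertial system, and wrist sensor worn by the participant". It introduces the 3-sensor set (both feet and trunk) only for visits held at home.
- In the Schedule of Activities (1.2), the mark on the 7-meter gait test "denotes that these tasks will be performed while wearing lumbar sensors, wrist sensors, and 8-sensors IMU system". The mark on the 3-sensor heading ties that system to home testing when in-lab visits cannot take place.
- Section 6.1.1 introduces the in-lab functional tests with the remark that "only wrist and lumbar sensors will be worn during these tests".
- Pointing the other way, the substudy introduction says participants wear a 3-sensor system as well as the lumbar sensor, without naming a visit. The functional-assessment table in 6.1.1 also has a 3-sensor column.

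On timing, the protocol says: "The order of these assessments will be randomized and occur within 2-weeks of each other". The in-lab baseline visit is in week -1. PT starts in week 1, with two visits a week at first.

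**The concern.** Aim 2 is there to show how closely remote testing reproduces lab testing, for use when in-lab assessment is not feasible (SAP 1). That needs the same device, and a participant in the same state, at both visits.

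A site that follows the visit instructions to the letter fits the 8-sensor system in-lab and the 3-sensor system at home. The in-lab 3-sensor metrics then do not exist, or they come from another sensor set by a derivation nobody has defined. No text gives the placement of the eight sensors or a rule for taking 3-sensor metrics from them. No participant is described as wearing both systems in the same test, so a system offset could not be estimated directly later, and data never collected cannot be recovered.

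The timing question is smaller. If some at-home tests follow the first PT sessions, part of the home-minus-lab difference may be early treatment effect. This can happen in one visit order only, and SAP 4.5 has no term for order or PT exposure.

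**Working it through.** **1. The plan's own figure.** Protocol 6a sizes the substudy at 11 from a null ICC of 0.42, an ICC of 0.85, one-sided alpha 0.05, power 0.80 and k = 2 measurements. The standard formula for testing an ICC is n = 1 + 2k(z_alpha + z_beta)² / [(k − 1)(ln C0)²], with C0 = [1 + kρ0/(1 − ρ0)] / [1 + kρ1/(1 − ρ1)].

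- C0 = 2.448 / 12.333 = 0.1985, so (ln C0)² = 2.614.
- n = 1 + 4 × 6.183 / 2.614 = 10.46, which rounds up to 11. The stated figure reproduces.
- With 10% attrition, 11/0.9 = 12.2, stated as 12.

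This n was set for two at-home tests (Aim 1), so Aim 2 has no sample size of its own. Clarifying device and window does not change it.

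**2. Metrics exposed to the device conflict.** The 3-sensor columns hold 16 gait metrics (SAP Table 3) and 2 sit-to-stand metrics (Table 4), 18 in all. Nine have no lumbar counterpart: foot clearance, lateral step variability, three foot angles, three turning measures and stand-to-sit duration. The lumbar sensor is worn at both visits, so the lumbar columns carry no device change.

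**3. Calendar.** Assume that week 1 directly follows week -1, as the schedule columns show.

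- In-lab first: an in-lab visit on day -7 allows an at-home visit up to day 8, and one on day -1 up to day 14. The latest permitted date is therefore always in PT week 2, after about 2 to 4 sessions.
- Home first: the at-home visit precedes an in-lab visit in week -1, so it is always before PT.

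Protocol 6a expects 6 to 10 home-first participants, about half of the 12 to 20.

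**4. Size, by assumption only.** The documents give no offset. For gait speed, assume a between-person SD of 0.20 m/s (Vb = 0.04) and a like-for-like ICC of 0.85, so Ve = 0.04 × 0.15/0.85 = 0.00706. For a mean offset d with person-specific SD s, the absolute-agreement ICC is Vb / (Vb + Ve + d²/2 + s²/2).

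| Assumed offset (m/s) | d | s | ICC |
|---|---|---|---|
| 0.05 in everyone, varying by person | 0.05 | 0.05 | 0.807 |
| 0.10 in everyone, constant | 0.10 | 0 | 0.768 |
| 0.10 in everyone, varying by person | 0.10 | 0.05 | 0.750 |
| 0.10 in half (PT, in-lab-first only) | 0.05 | 0.05 | 0.807 |
| 0.05 in half (PT, in-lab-first only) | 0.025 | 0.025 | 0.839 |

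The half-width of the limits of agreement is 1.96 × sqrt(2Ve + s²). It is 0.233 m/s with s = 0 and 0.253 m/s with s = 0.05. The Bland-Altman bias moves by d itself. SAP 4.5 does not say which ICC form is meant. Under a consistency form, d drops out, and s = 0.05 gives 0.04 / (0.04 + 0.00706 + 0.00125) = 0.828.

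**The case against.** A reader might infer that location is definitely mixed with device and treatment throughout Aim 2, so that no disagreement could be attributed to location and sound remote testing would look poor. The documents do not support that, for four reasons.

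- **Intent.** The Table 3 title expects in-lab 3-sensor data. The table in Protocol 6.1.1 lists 3-sensor metrics for the 6-minute walk, which is done only in-lab. The substudy introduction does not limit the 3-sensor set to home. The Table 4 title is weak evidence, because it also covers the lumbar column and that sensor is plainly worn in-lab. The eight sensors may include feet and trunk.
- **Scope.** The lumbar sensor is the same in both places and is analysed on its own.
- **Timing.** Protocol 6a and section 10 call the at-home visit a baseline visit, which suggests it was meant to precede PT. Exposure needs the in-lab-first order and a late visit. Because order is randomized, PT is not fully tied to location.
- **Size.** Even the least favourable ICC above, 0.750, stays in the top band of SAP 4.2 A (0.75 to 1).

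All four stand as limits on the claim. They do not remove the contradiction. Intent shown in a table is not an instruction to fit the sensors, and the visit text that staff would follow says otherwise. Nor does any text require both visits to come before PT.

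**Conclusion.** The point holds as an unresolved inconsistency with a data consequence, not as established confounding. If the visit text is followed literally, the 18 3-sensor metrics have no valid in-lab half for Aim 2, and nine of them have no lumbar substitute. If the apparent intent is followed, the device problem disappears. The documents do not say which will happen.

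The open window is a separate and smaller point. It affects at most the in-lab-first participants, about half of 12 to 20, and only those tested late. A shift from either source enters the Bland-Altman bias directly: in full if everyone is shifted, by half if half are. The ICC effect may be modest, about 0.75 to 0.81 for the assumed offsets in everyone and 0.81 to 0.84 for the same offsets in half. These figures rest on an assumed SD, assumed offsets and an absolute-agreement ICC. No primary or secondary analysis is touched. It should be corrected because missing in-lab data cannot be recovered and the correction is cheap.

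**What to change.** - In Protocol 6a (substudy in-lab visit) and SAP 4.5, state that substudy participants wear the same 3-sensor set, on both feet and trunk, for the in-lab 7-meter gait and 5 times sit-to-stand tests. Alternatively, if the 8-sensor set includes those positions, state that the in-lab metrics come from those three sensors only, processed with the same software.
- Reconcile the sensor remark in Protocol 6.1.1 and the title of SAP Table 4 with that choice.
- Schedule both substudy assessments before PT visit 1, within the existing 2-week limit. Flag any pair that straddles PT visit 1 and report Aim 2 agreement with and without such pairs. Reporting both ways avoids losing participants from an already small sample.

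The cost is protocol and SAP wording, a few minutes of extra sensor set-up and slightly tighter scheduling for 12 to 20 participants.
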